9.5 Justification for future studies

- 9.5.1 After study accrual, patient safety data will be analyzed to ensure treatment was well tolerated. If found to be acceptable, a larger Phase II study powered to detect a 15% increase in local control rates as compared to historical control, with a power of 80% and alpha of 0.1 would be initiated.

10.0 Pathology Review

Post-stereotactic body radiation therapy pathology will be obtained at the time of microwave ablation and compared to the samples obtained prior to treatment. This will be obtained in order to complete the correlative studies described above and to determine tumor response to radiotherapy treatment. These pre-ablation samples are collected for research purposes only and no tissue will be submitted to the UW Pathology department for clinical use.

Analysis of research samples

-Samples will be processed and scored per standard institutional practices University of Wisconsin Carbone Cancer Center Translational Science BioCore (TSB-BioBank). Paraffin embedded, cryo-embedded, and fresh frozen sections will be stored.

-Future analysis by the study team will include H&E staining and evaluation for percentage of viable tumor remaining as measured by the presence of necrosis, fibrosis, hyalinization, and/or calcification, and immune cell infiltration and compared to pre-SBRT pathology obtained at the time of original tumor diagnosis.

Tumor samples will be sent to the TSB-BioBank, University of Wisconsin Hospital Carbone Cancer Center, [name] per standard procedures

11.0 Data Collection/Storage/Confidentiality

Clinical trial coordinators in the Department of Human Oncology will do baseline data collection for each patient accrued into the protocol. The PIs, with the support of co-

investigators would collect specific disease, treatment and outcome related data, which will include:

Medical history including basic patient demographics as collected during registration, comorbidities/habits and disease related variables including ECOG performance score, histological differentiation, tumor location, maximal tumor dimension as measured on diagnostic CT imaging, presence or absence of regional LN on diagnostic imaging, presence of metastatic disease at diagnosis, other pertinent findings on diagnostic imaging, stage, weight loss at presentation, baseline pain assessment, baseline laboratory parameters, treatment details, toxicity outcomes, treatment outcomes (clinical, radiological), and follow-up course.

The information collected for this study will be protected by limiting access to the data sheet to the study researchers. To ensure patient confidentiality information collected in this study will be kept on a secure computer within the Department of Radiation Oncology network, which is protected by a firewall that ensures the privacy of the network. Access to the information is limited to those listed in the protocol, all of whom have completed the requisite human subjects/HIPAA training and been given valid clinical access to this information.

Each subject will be assigned a research subject number, which is a code that can link the medical record number to the study data in the subject log. The subject log will be maintained on a secure password protected computer in the Department of Human Oncology. In addition to the principal investigators, the co-investigators will have access to the subject log.

12.0 Patient Consent and Peer Judgment

Current FDA, NCI, state, federal, and institutional regulations regarding informed consent will be followed.

13.0 Safety Monitoring

13.1 Adverse Event List for SBRT

Likely

- Gastritis
- Nausea and vomiting
- Diarrhea
- Fatigue
- Loss of appetite and weight loss
- Mild radiation dermatitis

Less likely

- Pigmentation changes and fibrosis in the cutaneous, subcutaneous and deep visceral tissues in the radiation field
- Musculo-skeletal aches in the treatment fields.

Decrease in blood counts resulting in increased risk of infection, weakness, and/ or in bleeding and bruising easily

Hematuria

Rare but serious late effects

Bowel obstruction

Gastric, duodenal or small-bowel ulceration or perforation

Hepatotoxicity

Chronic Kidney Injury

Renal Hemorrhage

Transient myelopathy

Second malignancy

13.2 Adverse Event List for Microwave Ablation/Biopsy

Likely

Pain

Paresthesia

Post-ablation syndrome

Nausea

Vomiting

Malaise

Fever

Hematuria

Acute Kidney Injury

Less Likely

Hemorrhage

Hematoma

Rare but serious late effects

Bladder outlet obstruction

Bowel perforation or ulceration

Nephrotoxicity

Myelopathy

Chronic Kidney Injury

Ureteral damage

Tumor seeding

13.25 Adverse Event List for Biospy

Likely

Pain

Infection

A general feeling of discomfort

Blood in urine

Less Likely

Bleeding that requires a transfusion

Blood clot in the kidney

Rare but serious late effects

Difficulty passing urine due to damage to the kidneys and ureters

Permanent tingling/numbness in the area treated due to nerve damage

13.3 Adverse events characteristics

The descriptions and grading scales found in the revised NCI Common Terminology Criteria for Adverse Events (CTCAE) version 5.0 will be utilized for AE reporting. A copy of the CTCAE can be downloaded from the CTEP web site (<http://ctep.cancer.gov>).

‘Expectedness’: AEs can be ‘Unexpected’ or ‘Expected’ for expedited reporting purposes only.

Attribution of the AE:

Definite – The AE *is clearly related* to the study treatment.

Probable – The AE *is likely related* to the study treatment.

Possible – The AE *may be related* to the study treatment.

Unlikely – The AE *is doubtfully related* to the study treatment.

Unrelated – The AE *is clearly NOT related* to the study treatment.

13.4 Adverse Event Reporting

Adverse events (AEs) and serious adverse events (SAEs) will be recorded in study database. All SAEs will be reported to the GU DOWG, UWCCC, and UW HS-IRB per policy. Reporting criteria are summarized in Table 3.

An AE is an undesirable medical occurrence (sign, symptom, or diagnosis) or worsening of a pre-existing medical condition (diabetes, congestive heart failure, rheumatoid arthritis) that occurs after initiation of the investigational product whether or not it is considered to be investigational product related. A worsening of an existing medical condition is one that was present at baseline (e.g., cancer, diabetes, migraine headaches, gout) and became more severe, more frequent, or increased in duration during investigational product treatment.

Expected events - Expected events are those that have been previously identified as resulting from treatment of renal cell cancer with radiation and MWA. These are defined above for acute and late toxicities (section 13.1). For purposes of this study, reporting requirements are determined by the assessment of the following adverse event characteristics: the type or nature of the event; the severity (grade); the relationship to the study therapy (unrelated, not likely, possibly, likely, or definitely related), and whether the event is expected or unexpected.

Recommended assessment steps include:

- Identification of adverse event.
- Determine whether the adverse event is expected or unexpected.
- Grading the severity of the adverse event using the appropriate set of criteria; CTCAE v5.0 (General, unexpected).
- Determination as to whether the adverse event is related to the study therapy using the following categories: Unrelated, Possible, Probable, and Definite

For the purpose of this study adverse event information will be collected through 30 day post MWA visit. After the 30 day visit only events specific late treatment effects will be collected.

We will continue to collect information on gastric, duodenal bowel and bladder ulcerations, perforations and obstructions, nephrotoxicity, myelopathy, ureteral damage tumor seeding and second malignancy's

An SAE is defined by regulatory agencies as one that suggests a significant hazard or side effect, regardless of the investigator or sponsor's opinion on the relationship to investigational product. This includes, but may not be limited to, any event that (at any dose):

1. Is fatal
2. Is life threatening (places the subject at immediate risk of death)
3. Requires inpatient hospitalization or prolongation of existing hospitalization
4. Is a persistent or significant disability/incapacity
5. Is a congenital anomaly/birth defect
6. Any event that does not exactly meet this definition yet, in the investigator's opinion represents a significant hazard can be assigned the "other significant hazard" regulatory reporting serious criteria
7. Additionally, important medical events that may not be immediately life threatening or result in death or hospitalization but that may jeopardize the subject or require intervention to prevent one of the outcomes listed above, or result in urgent investigation, may be considered serious. Examples include allergic bronchospasm, convulsions, and blood dyscrasias.

Note: All deaths on treatment require both routine and expedited reporting regardless of causality. Attribution to treatment or other cause must be provided. "On treatment" is defined as during or within 30 days of completing protocol treatment (MWA).

All serious adverse events deemed to be related by the investigator to the SBRT or MWA (as listed in section 13.) will be collected and recorded throughout the study period beginning with the signing of the informed consent through the day patient is removed from the study or the date of death or three years after completion of the MWA (or the last SBRT treatment if surgery is not performed), whichever is earlier.

All serious adverse events that occur after the subject has signed the informed consent form must be reported to University of Wisconsin Carbone Cancer Center Data Safety and Monitoring Board and other regulatory agencies.

Serious adverse events occurring after conclusion of the study AND thought to be possibly related to the investigational study will be collected and reported within 10 working days of discovery or notification of the event via the same mechanism.

Table 3. Expedited reporting requirements for adverse events that occur within 30 days of the last protocol intervention.

FDA Reporting Requirements for Serious Adverse Events (21 CFR Part 312)
--

NOTE: Investigators **MUST** immediately report to the PI, *UWCCC and UW IRB per policy* ANY Serious Adverse Events, whether or not they are considered related to the investigational agent(s)/intervention (21 CFR 312.64). FDA Med Watch (3500A) will be submitted for grade 4 and 5 events at the discretion of the sponsor-investigator.

An adverse event is considered serious if it results in ANY of the following outcomes:

- 1) Death.
- 2) A life-threatening adverse event.
- 3) An adverse event that results in inpatient hospitalization or prolongation of existing hospitalization for ≥ 24 hours.
- 4) A persistent or significant incapacity or substantial disruption of the ability to conduct normal life functions.
- 5) A congenital anomaly/birth defect.
- 6) Important Medical Events (IME) that may not result in death, be life threatening, or require hospitalization may be considered serious when, based upon medical judgment, they may jeopardize the patient or subject and may require medical or surgical intervention to prevent one of the outcomes listed in this definition (FDA, 21 CFR 312.32; ICH E2A and ICH E6).

ALL SERIOUS adverse events that meet the above criteria* **MUST** be immediately reported to the UWCCC within the timeframes detailed in the table below: With the exception of a 24 hr hospitalization for MWA procedure

Hospitalization	Grade 1 and Grade 2 Timeframes	Grade 3 Time Frames	Grade 4 & 5 Timeframes
Resulting in hospitalization ≥ 24 hrs	Not required	10 Calendar Days	24 Hour; 5 Calendar Days
Not resulting in Hospitalization ≥ 24 hrs	Not required	10 Calendar Days	

- See section 13.0 for listing of toxicities
- Grade 3 toxicities during the 24hr hospitalization for MWA are exemption from SAE reporting

Expedited AE reporting timelines are defined as:

- **24-Hour; 5 Calendar Days** – The AE must initially be reported within 24 hours of learning of the AE, followed by a complete expedited report within 5 calendar days of the initial 24-hour report.
- **10 Calendar Days** – A complete expedited report on the AE must be submitted within 10 calendar days of learning of the AE

¹Serious adverse events that occur more than 30 days after the last administration of investigational intervention and have an attribution of possible, probable, or definite require reporting as follows:

Expedited 24-hour notification followed by complete report within 10 working days for:

- All Grade 4, and 5 AEs

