- Appendix 1: Eligibility Checklist
- Appendix 2: UWCCC Data Safety Monitoring plan

1. Protocol Summary

Renal cell carcinoma is traditionally managed via a surgical approach. Increasingly, local therapy with radiofrequency and microwave ablation is being utilized as an alternative for patients who may not tolerate a nephrectomy or who refuse one. Although local control rates for small lesions are excellent, they drop off precipitously for lesions over 4 cm. Furthermore, lesions in critical areas such as the renal hilum may be difficult to treat with this method. Stereotactic body radiation therapy (SBRT) has had a long record of treating patients with inoperable tumors in locations such as the lung and central nervous system, and there is increasing evidence that it may be useful for patients with renal cell carcinoma. The recent emergence of MRI-guided radiation therapy allows for direct visualization of tumors during treatment, and may potentially allow clinicians to treat tumors more precisely. This phase I study will treat renal cell carcinoma patients using a combination of MRI-guided stereotactic body radiation therapy and microwave ablation.

The specific aims of this study are:

1. To determine the safety and feasibility of treating patients with a combination of MRI-guided stereotactic body radiation therapy and microwave ablation.
2. To assess short and long-term toxicity rates of patients treated with a combined modality approach.
3. To assess local control, survival, and pathologic response to treatment

2. Introduction

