6.7 Duration of Therapy

Treatment with SBRT will be delivered over a period of two weeks, with radiation delivered two to three times per week. Four to six weeks after treatment, patients will be evaluated for microwave ablation by the treating radiologist with repeat CT or MRI imaging of the abdomen. Eight weeks after the conclusion of radiation treatment, patients will undergo microwave ablation, a single procedure. Adjuvant systemic treatment will be administered per institutional policies, physician recommendations, and patient preferences. Criteria for removal from study are described below.

6.8 Duration of Follow-Up: Refer to Table 2

After study enrollment, patients will undergo SBRT over a period of approximately 2 weeks. After 8 weeks, patients will undergo microwave ablation. Post treatment, patients will be followed as per standard of care. This will include a clinical visit four weeks after ablation, three months after ablation, six months after ablation, followed by visits every 6 months for a period of 3 years. Imaging will include either contrast-enhanced CT or MRI imaging at 3 and 6 months post therapy and every 6 months for 3 years. A BMP (including creatinine) will be obtained with imaging to evaluate renal function. Long term toxicity (specifically, nephrotoxicity, bowel obstruction, skin changes, and pain) will be assessed at these follow-up visits. Follow-up visits will be conducted by one of the treating physicians (radiation oncologist, interventional radiologist, or urologist) who will document physical exam, laboratory, and imaging findings as well as evaluate for toxicity. Any other evaluations prompted by symptoms, laboratory evaluation, or at the treating physicians' discretion may be performed as per standard of care. If a patient decides to withdraw from the study for non-treatment related reasons, no additional study-specific information will be obtained from the patient's future follow-up visit.

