7.1 Toxicity Assessment

- 7.1.1. Dose-limiting toxicity (DLT) will be defined as grade 4 non-hematologic/grade 5 toxicity attributable to treatment, occurring until 30 days after ablation. Patients will be monitored and assessed for unexpected long-term toxicity during the post-treatment followup period. In the case of unexpected long-term toxicity, the dose level will be evaluated and potentially used to recalculate the MTD. Potential toxicities due to stereotactic body radiation therapy and microwave ablation are listed in Section 13.1 and 13.2 respectively. The most likely acute side effects of treatment include fatigue, nausea, vomiting, and pain due to the procedure. Toxicities not caused by treatment, such as pain due to tumor progression, will be excluded from the assessment.

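### After the 30-day post-ablation visit, section 13.4 limits non-serious adverse event collection to a closed list that conflicts with sections 6.8, 7.1.1, 13.1, 13.25 and Table 2

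*Combined protocol and SAP*

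**What the plan says.** Section 13.4 sets the general rule: "For the purpose of this study adverse event information will be collected through 30 day post MWA visit". It then narrows collection: "After the 30 day visit only events specific late treatment effects will be collected". The effects that continue to be collected are "gastric, duodenal bowel and bladder ulcerations, perforations and obstructions, nephrotoxicity, myelopathy, ureteral damage tumor seeding and second malignancy".

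Other parts of the protocol ask for more:

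- Section 1, aim 2: "To assess short and long-term toxicity rates of patients treated with a combined modality approach".
- Section 6.8: "Long term toxicity (specifically, nephrotoxicity, bowel obstruction, skin changes, and pain) will be assessed at these follow-up visits".
- Section 7.1.1 promises monitoring for unexpected late toxicity throughout follow-up and gives it a use: "In the case of unexpected long-term toxicity, the dose level will be evaluated and potentially used to recalculate the MTD".
- Section 13.1 names "Hepatotoxicity" and "Renal Hemorrhage" among the rare but serious late effects of SBRT.
- Section 13.25 names lasting tingling or numbness from nerve damage among the late effects of biopsy.
- Table 2 marks adverse event evaluation at the follow-up visits, with no restriction to particular events.

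Section 13.4 also has separate provisions for serious adverse events (SAEs). Related SAEs are collected for up to three years after MWA, all SAEs after consent are to be reported, and a footnote to Table 3 covers attributable grade 4 and 5 SAEs more than 30 days after the last intervention.

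**The concern.** Long-term toxicity rates are a stated aim, and nearly all of the follow-up lies beyond the point at which full collection ends. Two gaps need to be kept apart.

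The first concerns named late effects. The protocol says in one place that they will be assessed, or lists them as known risks, and in another leaves them off the list of what is collected. Staff working from 6.8 would record late skin changes and pain; staff working from 13.4 would not. The reported rates would then depend on which section was followed.

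The second concerns unexpected events. A closed list of named effects cannot hold an event that nobody anticipated. Section 7.1.1 sets no seriousness or grade threshold for the late toxicity that may prompt a second look at a dose level, so part of what it calls for has no collection route under 13.4.

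**Working it through.** The plan gives no figure to reproduce here. The check is a comparison of lists, then a search for other collection routes, then an illustration of scale.

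**Step 1. Each source against the 13.4 list.** Chronic kidney injury is counted as covered by nephrotoxicity, and transient myelopathy by myelopathy.

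| Source | Late items | Not on the 13.4 list |
|---|---|---|
| 6.8 | 4 | 2: skin changes, pain |
| 13.1, late effects | 7 | 2: hepatotoxicity, renal hemorrhage |
| 13.2, late effects | 7 | 0 |
| 13.25, late effects | 2 | 1: lasting tingling or numbness |
| 7.1.1 | open category | the whole category |
| Table 2 | unrestricted | everything unlisted |

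If chronic kidney injury is not read as nephrotoxicity, the 13.1 count becomes 3 of 7 and the 13.2 count 1 of 7. The mismatch runs both ways: of the 13.4 items, 6.8 names only nephrotoxicity and bowel obstruction. Hemorrhage is also one of the events named in the dose-limiting toxicity (DLT) definition in 6.2.2, so the late form of a DLT event is unlisted.

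**Step 2. Other routes after 30 days.** The SAE provisions described above take in serious late events, listed or not. What has no route under 13.4 is a late event that is both non-serious and unlisted. Late skin change, chronic pain, numbness or a laboratory liver abnormality can all occur without meeting an SAE criterion.

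One point in the SAE route is unclear. The three-year sentence carries a parenthesis referring to events as listed in section 13. If that limits its scope, an unexpected related SAE rests on the sentence requiring all SAEs after consent to be reported and, for grades 4 and 5, on the Table 3 footnote.

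**Step 3. Share of follow-up affected.** Full collection covers 30 days of about 3 years (1,096 days) after MWA: 30 / 1,096 = 2.7%. About 97% of post-MWA follow-up falls under the restricted list plus the SAE route.

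**Step 4. Illustration.** The chance that at least one of *n* patients has a toxicity with true rate *p* is 1 − (1 − *p*)^*n*. Both inputs are assumptions. The documents give no late event rate, so *p* is taken as 5-10%. The number at the MTD depends on escalation: 3 or 6 Phase IA patients, plus 10 if the optional Phase IB is run.

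| Patients at the MTD | p = 5% | p = 10% |
|---|---|---|
| 3 (no Phase IB) | 1 − 0.95^3 = 14% | 1 − 0.90^3 = 27% |
| 6 (no Phase IB) | 1 − 0.95^6 = 26% | 1 − 0.90^6 = 47% |
| 13 (3 + 10) | 1 − 0.95^13 = 49% | 1 − 0.90^13 = 75% |
| 16 (6 + 10) | 1 − 0.95^16 = 56% | 1 − 0.90^16 = 81% |

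These are chances that there is something to record, not chances that it is missed. Whether it is missed depends on which section is followed.

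**The case against.** A focused late-effects list is a legitimate choice in a small phase I trial, and the SAE provisions do most of the protective work. A reader might infer that nothing outside the list is recorded after 30 days, or that late events not judged related are lost. For serious events the documents say otherwise: the sentence covering all SAEs after consent has no attribution test and no 30-day limit.

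A reader might also infer that the safeguard in 7.1.1 is disabled. That goes too far. DLTs are grade 4 or higher and 6.2.2 excludes grade 3. Late events that are fatal, life-threatening or need hospital admission meet the SAE definition, so most late events that bear on the MTD are captured. The DLT window itself closes 30 days after ablation, within full collection, so the primary endpoint is untouched.

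Nor are the named omissions themselves the trigger in 7.1.1. Section 13.4 defines expected events by reference to 13.1, which lists hepatotoxicity and renal hemorrhage and includes skin and musculoskeletal effects.

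Finally, a recorded rate of zero for unlisted events is not certain. Section 6.8 has the treating physician evaluate toxicity at each visit, Table 2 schedules the evaluation, and section 11 collects toxicity outcomes. A zero follows only if 13.4 overrides them.

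All of this stands, and it limits the point to non-serious late toxicity. It does not remove the conflict: 13.4 states an exclusive rule, other sections contradict it, and nothing says which governs.

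**Conclusion.** The point holds in a limited form. Section 13.4 contradicts 6.8 and Table 2 on what is collected late, omits late effects that 13.1 and 13.25 name, and leaves 7.1.1 without a route for non-serious unexpected late toxicity. Five named effects and one open category are affected. If 13.4 is followed literally, the rates of those toxicities under aim 2 are biased low, and non-serious unexpected events do not reach the 7.1.1 review. Serious late events and the DLT endpoint are not affected.

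The item counts rest on reading nephrotoxicity as including chronic kidney injury. The illustrative 49-75% (13 patients) and 56-81% (16 patients) rest on an assumed 5-10% rate and on Phase IB being run; without it the figures are lower. This should be corrected, but it does not threaten the dose-escalation design.

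**What to change.** - Use a single late-effects list in 6.8 and 13.4. It should combine the 6.8 items, the current 13.4 items, and the entries under the late-effects headings only of 13.1, 13.2 and 13.25. Taking in the whole of 13.1 and 13.2 would add acute effects such as nausea and fever for three years to no purpose.
- Add an open line for any other late toxicity at least possibly related to SBRT or MWA, with CTCAE grade and attribution, and name it in 7.1.1 as a source for that review. At minimum it should take grade 3 or higher. With that minimum, unlisted grade 1-2 late toxicity would still go unrecorded, and the protocol should say so.
- Record the list to 3 years at the follow-up visits where Table 2 already schedules adverse event evaluation.
- State that the parenthesis in the three-year SAE sentence does not exclude unexpected related SAEs.

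The cost is about six added case report form lines: skin changes, pain, hepatotoxicity, renal hemorrhage, lasting tingling or numbness, and the open line. No new visits are needed.

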6.6 Tissue Sampling

Clinical pathologic evaluation

At the time of the initial diagnostic biopsy, a four quadrant biopsy will be performed per normal procedures. All tissue from the four quadrant biopsy will be processed per normal UW pathology procedures.

Research tissue sampling

If a clinical biopsy confirming renal cell cancer has not yet been performed, at the time of the clinical biopsy, 3 additional core biopsy samples will be obtained for research purposes. The samples will allow for creation of paraffin embedded, cryo-embedded and fresh frozen sections for evaluation of SBRT treatment response prior to microwave ablation.

During the microwave ablation procedure, 3 core biopsy samples will be obtained for research purposes. The primary tumor will be assessed for percent residual viable cells, the ratio of residual viable tumor to parenchyma, ratio of fibrotic stroma to tumor mass in the resected specimen, and immune cell infiltration, by the study team at a later date.

The research samples will be obtained and stored by the University of Wisconsin Carbone Cancer Center Translational Science BioCore (TSB-BioBank, University of Wisconsin Hospital Carbone Cancer Center, [name]). The BioBank utilizes ONCORE for “registration” of the samples to the BioBank. Actual samples study samples(research core samples) will be coded with the study number, case # assigned by Radiation Oncology staff, and timepoint: 1 (pre-treatment) or 2 (post- XRT). All BioBank staff have undergone required human subjects training and HIPAA training. Actual specimens will be located within the BioBank in a room that is card access controlled with monitoring.

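### Section 13.4 makes SAE collection depend on investigator-judged relation to SBRT or MWA from consent onward, against the plan's own all-SAE rules; the exposed events lie before SBRT and more than 30 days after MWA

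*Combined protocol and SAP*

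**What the plan says.** Protocol section 13.4 contains several rules on serious adverse events (SAEs):

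- **Opening.** AEs and SAEs go into the study database, and SAEs are reported to the GU DOWG, UWCCC and the IRB. There is no relatedness condition.
- **Collection sentence.** "All serious adverse events deemed to be related by the investigator to the SBRT or MWA", with a pointer to the section 13 lists, are collected and recorded from consent "through the day patient is removed from the study or the date of death or three years after completion of the MWA" (or after the last SBRT treatment if the later procedure is not done), whichever is earlier.
- **Following paragraph.** "All serious adverse events that occur after the subject has signed the informed consent form must be reported" to the cancer center's safety board. It has no relatedness condition and no end date. A further sentence deals with possibly related SAEs after the study has concluded.
- **Table 3.** Its title is "Expedited reporting requirements for adverse events that occur within 30 days of the last protocol intervention". Its note tells investigators to report "ANY Serious Adverse Events, whether or not they are considered related to the investigational agent(s)/intervention". Its footnote limits later reporting to events attributed as possible or higher, and lists grades 4 and 5.
- **Deaths.** Deaths up to 30 days after MWA are reported whatever the cause.
- **AE definition and window.** An AE is an event "that occurs after initiation of the investigational product whether or not it is considered to be investigational product related". General AE information is collected through the 30-day post-MWA visit; after that, only named late effects are.

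The UWCCC Data Safety Monitoring Plan appendix sends every SAE to the DSMC Chair. Its copy of the expedited table counts the 30 days from the last radiation dose.

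On biopsies, section 6.6 says "3 additional core biopsy samples will be obtained for research purposes" at the clinical biopsy if that biopsy has not yet been done. Three research cores are also taken during MWA. Sections 13.2 and 13.25 list biopsy events, including bleeding severe enough to need transfusion.

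**The concern.** An SAE that is not collected cannot be reported. A sentence that specifies collection of related SAEs sits next to one that demands reporting of all of them, and a coordinator has no text that says which governs. The natural compromise (all SAEs to 30 days, related ones afterwards) is not what the collection sentence says, because its relatedness condition begins at consent.

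The condition also names only SBRT and MWA, and the attribution scale in section 13.3 is defined against study treatment. Harm from a research procedure therefore has no clear place in either. What is at stake is the completeness of safety data in a phase I trial whose first aim is safety, including harm from cores taken for research.

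**Working it through.** The plan gives no figure on this point, so the check sets the rules side by side by period. All entries come from section 13.4 and Table 3, except where the appendix is named.

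| Period | Collection sentence | AE definition and window | Expedited tables | All-SAE rules (13.4 opening, following paragraph, appendix) |
|---|---|---|---|---|
| Consent to first SBRT fraction | Nothing can qualify | Not yet started | Table 3 states no start point | Every SAE |
| First fraction to 30 days after MWA | Related SAEs | Every AE, related or not | Table 3: any SAE. Appendix copy: any SAE to 30 days after last radiation dose, then attributed events | Every SAE |
| More than 30 days after MWA, to 3 years | Related SAEs | Named late effects only | Attributed events, grades 4 and 5 listed | Every SAE, no end date |

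**Before SBRT.** A serious complication of the research cores cannot be related to SBRT or MWA, because neither has been given. It also precedes the start of treatment that the AE definition requires. The all-SAE rules are the clear cover, and they are the rules the collection sentence contradicts. This arises only in patients whose diagnostic biopsy is still outstanding at consent (Table 2, note 3). The documents do not say how many that will be; the possible range is none to all of at most 28 patients.

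**First fraction to 30 days after MWA.** The collection sentence is narrower than its neighbors, but here it is not the only route into the database. AEs are recorded whether or not they are judged related, through the visit that closes the DLT window (sections 6.2.2 and 9.3.1).

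**After 30 days.** An SAE judged unrelated, and not one of the named late effects, is outside the collection sentence, the continuing AE collection and the Table 3 footnote. Again only the all-SAE rules reach it.

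**Appendix window.** MWA is planned about 8 weeks after SBRT:

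- 8 × 7 = 56 days from the last fraction to MWA.
- 56 + 30 = 86 days to the end of the DLT window (section 6.2.2 says approximately 90).
- The appendix's unconditional window closes at day 30, which is 56 − 30 = 26 days before MWA.
- The remaining 86 − 30 = 56 days, MWA included, fall under the footnote limited by attribution.

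Table 3 counts from the last protocol intervention instead, so the two copies disagree over that stretch. Both copies mention the hospital stay for MWA, which suggests that the appendix window was not meant to end before MWA. This disagreement concerns expedited reporting, not whether the event is recorded.

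**The case against.** The strongest reply is that the collection sentence does not contain the word only, and that the plan states the wider duty several times: at the opening of 13.4, in the paragraph after the sentence, in the Table 3 note and in the appendix. On-treatment deaths are reported regardless of cause. Under intermediate monitoring, the appendix also describes DOWG meetings that discuss each subject's results, with semi-annual reports to the DSMC. A reader might infer that unrelated SAEs may never reach the safety committee. The documents do not support that: it would need staff to follow one sentence and disregard all the others. This part of the reply stands.

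It is also fair to say that biopsy harm is not simply left out. The collection sentence points to the section 13 lists, which include biopsy events, and one of the two research biopsies is done during MWA. A serious complication of the pre-SBRT cores is still covered by the paragraph on all SAEs after consent. That narrows the biopsy gap to the pre-SBRT procedure and to what happens if the narrower sentence is followed.

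Finally, Table 3 is not a rule for every SAE after consent. It runs for 30 days after the last protocol intervention, its grid asks for no report at grades 1 and 2, and it exempts grade 3 toxicities during the MWA stay. This also stands, and it is why the later period needs its own reconciliation.

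None of this removes the contradiction. A condition on relatedness has no purpose if every SAE is collected anyway.

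**Conclusion.** The point holds as an internal contradiction that should be reconciled. The collection sentence conflicts with the general all-SAE rules throughout, and with Table 3 within its 30 days. The consequence depends on staff following the narrower sentence. If they do, the SAEs most exposed are serious complications of the pre-SBRT research cores and unrelated SAEs more than 30 days after MWA. The documents give no rate for either, so no numerical size can be attached.

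Because DLT depends on attribution by study physicians (section 6.2.2), a reader might infer that the sentence could let a misattributed event slip past the 3+3 decision. The documents do not show this. Within the DLT window AE recording is independent of attribution, and DOWG review is a further check. A wrong attribution would change the 3+3 count whether or not an SAE form was filed. How sensitive the 3+3 is to misattribution is a separate question, and it does not measure this defect.

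**What to change.** 1. In the collection sentence, remove the relatedness condition. All SAEs from consent, including research-biopsy complications, are collected and recorded regardless of attribution at least to 30 days after MWA, or after the last SBRT treatment if MWA is not done.
2. For the later period, reconcile the collection sentence, the open-ended all-SAE paragraph and the Table 3 footnote. The new text should not shorten the all-SAE duty that now has no end date. The footnote lists only grades 4 and 5, so it cannot serve as the rule for all later SAEs.
3. Start AE and SAE capture for research biopsies at the procedure, so that the AE definition does not exclude the pre-SBRT cores.
4. Align the appendix table with Table 3, so that both count 30 days from the last protocol intervention.

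The cost is a short wording change in section 13.4 and the appendix, plus a few more SAE forms in a trial of at most 28 patients. Treatment and the escalation rules are unaffected.
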